11.11 Appendix 11: Country Specific Requirements

Germany: a CXR or CT scan must be available in the 12 months prior to Screening for eligibility.

1. INTRODUCTION

This document describes the rules and conventions to be used in the presentation and analysis of efficacy and safety data for Protocol RPL554-CO-301. It describes the data to be summarized and analyzed, including specifics of the statistical analyses to be performed.

This statistical analysis plan (SAP) is based on protocol version 6.0, dated 18 February 2022.

A separate pooled SAP will be created which will include the details of pooled analysis between RPL554-CO-301 and RPL554-CO-302.

There will also be a separate blinded data review (BDR) plan that will outline the process for identification and decision making on patient's exclusion from analysis sets and on major protocol deviations. These will then be summarized in BDR report created for the data review outputs. This document will summarize each analysis set and reasons for the exclusion. In the BDR report protocol deviations (PDs) will also be outlined, specifying which patients were identified with each PD and whether these led to exclusion from the PP population. All analysis sets will be defined, and all possible PDs will be identified prior to unblinding.

[REDACTED]

2. STUDY OBJECTIVES AND ESTIMANDS

2.1. PRIMARY OBJECTIVE

The primary objective of this study is to evaluate the efficacy of ensifentrine on lung function compared to placebo over a 12-hour dosing interval in patients with moderate to severe chronic obstructive pulmonary disease (COPD).

2.2. SECONDARY OBJECTIVES

- To evaluate the effect of ensifentrine on other lung function parameters.
- To evaluate the effect of ensifentrine on COPD symptoms.
- To evaluate the effect of ensifentrine on health-related quality of life.

2.3. OTHER OBJECTIVES

- To evaluate the effect of ensifentrine on moderate/severe COPD exacerbations.
- To evaluate the effect of ensifentrine on health utility and healthcare resource utilization (HRU).

2.4. SAFETY OBJECTIVES

To evaluate the safety and tolerability of ensifentrine over 24 and 48 Weeks.

2.5. ESTIMANDS

The primary and secondary estimands to support regulatory decisions are described in Table 1.

[REDACTED]	[REDACTED]	[REDACTED]	[REDACTED]
[REDACTED]	[REDACTED]	[REDACTED]	[REDACTED]
[REDACTED]	[REDACTED]	[REDACTED]	[REDACTED]
[REDACTED]	[REDACTED]	[REDACTED]	[REDACTED]

Table 1: List of Estimands

Estimand	Definition	Attributes			
		Population	Variable/ Endpoint	Intercurrent event handling strategy	Population-level summary measure
Primary	The efficacy of ensifentrine on lung function compared to placebo over a 12-hour dosing interval in patients with moderate to severe COPD.	Patients with moderate to severe COPD aged 40-80 years (inclusive) that are in the modified intent-to-treat (mITT) population. See full list of inclusion and exclusion criteria in Sections 5.1, 5.2 and 5.3 of study protocol.	Change from baseline forced expiratory volume in 1 second (FEV ₁) to average FEV ₁ area under the curve over 12 hours (AUC _{0-12h}) at Week 12.	Regardless of whether the patient discontinues treatment prematurely and regardless of major protocol deviation, as per the Treatment Policy strategy.	Estimated treatment difference at Week 12 of the double-blind period (and corresponding 95% confidence interval [CI]) from analysis of covariance (ANCOVA) analysis.
Secondary	To evaluate the effect of ensifentrine on other lung function parameters.	Patients with moderate to severe COPD aged 40-80 years (inclusive) that are in the mITT population. See full list of inclusion and exclusion criteria in Sections 5.1, 5.2 and 5.3 of study protocol.	
 Change from baseline FEV₁ to average FEV₁ AUC_{0-4h} at Week 12 Change from baseline FEV₁ to peak FEV₁ at Week 12 Change from baseline FEV₁ to morning trough FEV₁ at Week 12 	Regardless of whether the patient discontinues treatment prematurely and regardless of major protocol deviation, as per the Treatment Policy strategy.	Estimated treatment difference at Week 12 of the double-blind period (and corresponding 95% CI) from ANCOVA analysis.

Secondary	To evaluate the effect of ensifentrine on COPD symptoms.	Patients with moderate to severe COPD aged 40-80 years (inclusive) that are in the mITT population. See full list of inclusion and exclusion criteria in Sections 5.1, 5.2 and 5.3 of study protocol.	Change from baseline (i.e. mean over the last 7 days of run-in) to the mean weekly value at Week 24 in COPD symptoms, as measured by daily diary (Evaluating Respiratory Symptoms for COPD [E-RS™;COPD])	Regardless of whether the patient discontinues treatment prematurely and regardless of major protocol deviation, as per the Treatment Policy strategy.	Estimated treatment difference at the end of the double-blind period (and corresponding 95% CI) from ANCOVA analysis.
Secondary	To evaluate the effect of ensifentrine on health-related quality of life.	Patients with moderate to severe COPD aged 40-80 years (inclusive) that are in the mITT population. See full list of inclusion and exclusion criteria in Sections 5.1, 5.2 and 5.3 of study protocol.	
 1. Change from baseline in the St. George's Respiratory Questionnaire (SGRQ) total score at Week 24 2. Proportion of SGRQ responders at Week 24 	Regardless of whether the patient discontinues treatment prematurely and regardless of major protocol deviation, as per the Treatment Policy strategy.	
 1. Estimated treatment difference at the end of the double-blind period (and corresponding 95% CI) from ANCOVA analysis. 2. Odds ratio for proportion of responders with an improvement of at least 4 units at the end of the double-blind period (and corresponding 95% CI) from logistic

[Redacted]
 [Redacted]
 [Redacted]
 [Redacted]
 [Redacted]
 [Redacted]

							regression analysis.
--	--	--	--	--	--	--	----------------------

[REDACTED]

[figure not shown]

3. STUDY DESIGN

3.1. GENERAL DESCRIPTION

This is a Phase III, multicenter, randomized, double-blind, parallel group, placebo-controlled study. A flow chart illustrating the key components of the study is provided in Figure 1:

Figure 1: Study Flow Chart

Approximately 800 patients with moderate to severe COPD aged 40 to 80 years (inclusive) will be stratified by three different factors: treatment duration (48 or 24 weeks), stable background maintenance long-acting muscarinic antagonist (LAMA) or long-acting beta-2 agonist (LABA) monotherapy use (yes or no) and cigarette smoking (current or former). The 48-week stratum will be randomized 3:1 to receive ensifentrine (3 mg):placebo, and the 24-week stratum will be randomized 1:1 to receive ensifentrine (3 mg):placebo. Patients in the background maintenance LAMA or LABA therapy strata must withhold twice-daily maintenance LAMA or LABA (or LAMA/ICS or LABA/ICS) for 24 hours and once-daily maintenance LAMA or LABA (or LAMA/ICS or LABA/ICS) for 48 hours prior to initiation of any spirometry. All patients must withhold short acting beta-2 agonist (SABA) rescue medication for at least 4 hours prior to initiation of any spirometry.

[REDACTED]

Patients are expected to take the study medication twice daily, administered via a standard jet nebulizer, during the study period. Schedule of in-clinic dosing can be found in Section 1.4 of the study protocol.

3.2. SCHEDULE OF EVENTS

Schedule of activities can be found in Section 1.3 of the study protocol.

3.3. CHANGES TO ANALYSIS FROM PROTOCOL

Changes to analysis from protocol include:

- “COPD severity” added as a subgroup analysis.
- Sections 9.4.1 and 9.4.4 in the protocol states, “A sensitivity analysis [on the proportion of responders on the SGRQ] will be performed in which patients with missing data at the required visit will be considered non-responder in the analysis”, and “For the responder analysis of SGRQ, patients with no available data for imputation will be considered non-responders as a sensitivity analysis”, respectively. However, a non-responder analysis may create an unintentional bias in favor of the treatment arm, i.e. if placebo patients discontinue, this technique may inadvertently set more values in the placebo arm to “non-responder”. Therefore, this technique for missing data analysis will not be implemented.
- Analysis of E-RS total score responder, defined as a decrease from baseline in the week mean total of E-RS score of greater than or equal to 2, added in the Section 16.3.1.6.
- Analysis of Morning trough FEV₁ responder, defined as an improvement from baseline of 100 mL or more, added in Section 16.3.1.7.
- Chronicity section removed from Adverse Event section.
- A sensitivity analysis will be performed for weekly mean E-RS total score, using ANCOVA approach, as described in Section **Error! Reference source not found.** of the SAP, in which all patients with baseline mean = 0 will be excluded.
- Due to unreliability of the data, sites [REDACTED] will be removed from efficacy and safety analyses in any section.
- Extended mITT and extended Safety populations set will be included as new populations to manage these sites being removed. Added in Section 5.
- Additional efficacy analysis of SGRQ and E-RS per domain using mITT population: SGRQ domains: Symptoms – items 1 to 8; Activity – items 11 and 15; Impacts – items 9, 10, 12, 13, 14, 16 and 17 and E-RS domains: Breathlessness – items 7, 8, 9, 10 and 11 (score range: 0-17); Cough and Sputum – items 2, 3 and 4 (score range: 0-11); Chest Symptoms – items 1, 5 and 6 (score range: 0-12)

[REDACTED]

[REDACTED]

[REDACTED]

[REDACTED]

[REDACTED]

4. PLANNED ANALYSES

A final analysis after database lock (DBL) is planned for this study.

4.1. DATA MONITORING COMMITTEE (DMC)

There will be no DMC for this study.

4.2. INTERIM ANALYSIS

There is no interim analysis planned for this study, however additional patients may be randomized if:

- the SD has increased significantly from the estimated 250 mL, as per sponsor discretion, and/or
- the withdrawal rate at 24 weeks exceeds 25% overall, and the percentage of patients with missing FEV₁ over 12 hours at Week 12 in mITT (modified Intent-to-Treat) population exceeds 20% overall.

Note: As part of the primary endpoint analysis, SD of the treatment difference is calculated to check the sample size with 90% power.

4.3. FINAL ANALYSIS

All final, planned analyses identified in this SAP will be performed by IQVIA Biostatistics following sponsor authorization of SAP (and associated output shells), DBL, analysis sets and unblinding of treatment.

5. ANALYSIS SETS

Agreement and authorization of patients included/excluded from each analysis set will be conducted prior to the unblinding of the study.

Analyses will be performed for the analysis sets described in Table 2.

[REDACTED]	[REDACTED]	[REDACTED]	[REDACTED]
[REDACTED]	[REDACTED]	[REDACTED]	[REDACTED]
[REDACTED]	[REDACTED]	[REDACTED]	[REDACTED]
[REDACTED]	[REDACTED]	[REDACTED]	[REDACTED]

Table 2: Analysis sets

	All Patients Enrolled Set	All Patients Random. Set	Extended Random. Set	Modified Intent-to-Treat Pop.	Extended modified Intent-to-Treat Pop.	Per-Protocol Pop.	Safety Set	Extended Safety Set
Disposition of patients	X	X	X					
Protocol deviations		X						
Demographic and other baseline characteristics		X	X	X	X			
Surgical and medical history							X	
Prior and concomitant medication							X	
Compliance							X	
Efficacy: Primary endpoint				X	X	X		
Efficacy: Secondary endpoint				X	X	X		
Efficacy: Other endpoints				X				
Sensitivity Analyses				X	X	X		
Safety							X	X

[REDACTED]

[REDACTED]

[REDACTED]

[REDACTED]

[REDACTED]

5.1. PROCESS FOR ANALYSIS SET ASSIGNMENT

Analysis set assignments and any associated reasons for analyses set exclusion will be described in the BDR plan and finalized within the BDR report prior to unblinding.

5.2. ALL PATIENTS ENROLLED SET

The all patients enrolled (ENR) set will contain all patients who provide informed consent for this study. Patients will be classified according to randomized treatment with patients not randomized presented in a separate category, see Appendix 1. All patients enrolled will be summarized with and without subjects consented at sites [REDACTED]

5.3. ALL PATIENTS RANDOMIZED SET

The all patients randomized (RND) set will contain all patients in the ENR set who were randomized to study medication. For analyses and displays based on RND, patients will be classified according to randomized treatment. Sites number [REDACTED] will be excluded from this population.

5.4. EXTENDED RANDOMIZED SET

The Extended RND set will contain all patients in the ENR set who were randomized to study medication. For analyses and displays based on RND, patients will be classified according to randomized treatment. Sites number [REDACTED] will be included in this population.

5.5. MODIFIED INTENT-TO-TREAT POPULATION

The mITT population will contain all patients in the RND set who received at least one dose (or partial dose) of study medication and patients will be classified according to randomized treatment. The intent-to-treat principle is preserved, despite the exclusion of patients randomized who did not take the study medication, because the decision of whether or not to begin the treatment could not be influenced by knowledge of the assigned treatment, i.e. the study medication is blinded. Sites number [REDACTED] will be excluded from this population.

5.6. EXTENDED MODIFIED INTENT-TO-TREAT POPULATION

The Extended mITT population will contain all patients in the RND set who received at least one dose (or partial dose) of study medication and patients will be classified according to randomized treatment. The intent-to-treat principle is preserved, despite the exclusion of patients randomized

[REDACTED]

who did not take the study medication, because the decision of whether or not to begin the treatment could not be influenced by knowledge of the assigned treatment, i.e. the study medication is blinded. Sites number [REDACTED] will be included in this population.

5.7. PER-PROTOCOL POPULATION

The per-protocol (PP) population will contain all patients in the mITT who did not discontinue the study medication before study day 74 and did not experience any major/important PDs considered to have an impact on efficacy assessments involving lung function at week 12. Reasons for exclusion will be specified at a BDR meeting prior to DBL and may include violations of inclusion/exclusion criteria, violations of withdrawal criteria, incorrect randomization, use of prohibited medication, did not follow blinding procedures and non-compliance. Patients will be classified according to randomized treatment. If protocol deviations in terms of dosing errors are detected post unblinding, these will lead to exclusion only if patient has received and used the opposite study drug compared to what was specified in the randomization and that this use occurred prior to week 12.

Patients who were excluded from PP due to the study medication being discontinued before study day 74 are not considered as protocol violations.

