9.3 Populations for Analyses

mITT population: will include all patients randomized and treated with blinded study medication in the study. Patients will be handled as randomized in the mITT analyses.

PP population: will include all patients in the mITT without any major/important protocol deviations considered to have an impact on efficacy assessments. Reasons for exclusion will be specified at a Blind Data Review Meeting prior to database lock (DBL) and may include violations of inclusion/exclusion criteria, violations of withdrawal criteria, incorrect randomization, use of prohibited medication and non-compliance.

Safety set: will include all patients randomized and treated in the study. Patients will be handled by actual treatment in the safety analyses.

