9.4 Statistical Analyses

9.4.1 Efficacy Analyses

Efficacy analysis will primarily be performed on the mITT population. The primary endpoint and key secondary endpoints will also be evaluated using the PP population as a sensitivity analysis. Impact of imputations and various baseline characteristics will also be checked.

The primary endpoint, change from baseline in FEV₁ AUC_{0-12h} at Week 12, will be compared between treatments using an analysis of covariance (ANCOVA) model adjusting for treatment, region, background medication strata, and smoking status as factors and baseline FEV₁ as covariate. The estimated treatment difference with 95% confidence interval and associated (two-sided) p-value will be presented. Missing data will be imputed to get as close to the mITT population as possible. Primarily imputation will be based on data collected at visits performed after treatment withdrawal or at early termination visits even if outside the visit window. When no such data is available, imputation will primarily be done using multiple imputation based on baseline characteristics and secondarily, as a sensitivity analysis, by the average change in the opposite treatment group as randomized to as a worst-case scenario. Further details on the handling of missing data will be given in the Statistical Analysis Plan.

Key secondary endpoints, FEV₁ AUC_{0-4h}, peak FEV₁, morning trough FEV₁, SGRQ total score and weekly mean E-RS total score, and other continuous secondary or exploratory endpoints will be assessed repeatedly during the study and the change from baseline to pre-specified time point of evaluation will be compared by similar ANCOVA models adjusting for treatment, region, background medication strata and smoking status as factors and baseline as covariate. Data collected at visits performed after treatment withdrawal or at early termination visits will be used in the analyses. Remaining missing data will primarily be imputed using multiple imputation based on baseline characteristics and data collected at post-randomization visits. Since assessed repeatedly, in contrast to primary endpoint, these data will also be analyzed for sensitivity by mixed model repeated measures models with treatment, visit and treatment by visit interaction as factors, baseline as covariate, subject as random factor and covariance structure by visit.

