7.4. MULTIPLE COMPARISONS/ MULTIPLICITY

To address multiplicity in the analysis of the endpoints, statistical testing of the primary endpoint and key secondary endpoints will be done in the hierarchical order (listed below). Initially the primary endpoint will be checked to see if comparison between active treatment and placebo is statistically significant. If yes, the first key secondary endpoint will be evaluated. If yes, the next key secondary endpoint will be evaluated. This process will continue until either all endpoints are evaluated, or if one of the endpoints' comparison is not significant.

Order of the endpoints that will be used for the hierarchical testing:

1. Change from baseline FEV₁ to FEV₁ AUC_{0-12h} at Week 12
2. Change from baseline FEV₁ to peak FEV₁ at Week 12
3. Change from baseline (i.e. mean over the last 7 days of run-in) to the mean weekly value at Week 24 in COPD symptoms, as measured by daily diary (E-RSTM:COPD)
4. Change from baseline in the SGRQ total score at Week 24
5. Change from baseline FEV₁ to morning trough FEV₁ at Week 12
6. Change from baseline FEV₁ to average FEV₁ AUC_{0-4h} at Week 12
7. Proportion of SGRQ responders at Week 24

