16.2.4. SENSITIVITY ANALYSIS OF SECONDARY EFFICACY VARIABLES

For the key secondary endpoints the following sensitivity analysis will be performed at Week 12.

- Subgroup analysis as specified in Section 7.5 of the SAP.
- ANCOVA analysis with average imputation, as described in Section 16.1.2 of the SAP.
- ANCOVA analysis with MI, only considering baseline and Week 12 (for lung function parameters) in the imputation model, as described in Section 16.1.2 and 16.1.3 of the SAP.
- ANCOVA analysis with MI using the range data method as described in Section 16.2.2.3 for SGRQ total score and weekly mean total E-RS.
- Tipping point approach, as described in Section 16.1.2 of the SAP.
- Analysis with MI method, as described in Sections 16.2.2 and 16.2.3 of the SAP, based on PP population.
- For FEV₁ key secondary endpoints (FEV₁ AUC_{0-4h}, peak FEV₁, morning trough FEV₁) additional sensitivity analysis will be performed:
 - MMRM model with treatment, visit and treatment by visit as fixed effect; baseline as covariate; patient as random factor; unstructured covariance by visit. If the model does not converge a compound symmetry covariance structure will be used. Kenward-Roger method will be used to estimate the model degrees of freedom.
 -
- For weekly mean E-RS total score and SGRQ total score, additional analysis will be performed:
 - For weekly mean E-RS total score at 6, 12 and 24 weeks using ANCOVA approach, as described in Section **Error! Reference source not found.** of the SAP, all patients with baseline mean = 0 will be excluded.
 - For SGRQ total score at 6, 12 and 24 weeks, using ANCOVA approach, as described in Section 16.2.3.1 of the SAP, all patients with baseline assessment done after dosing time and date will be excluded.
 -

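### The only per-protocol set is built for lung function at Week 12, so the three Week 24 key secondary endpoints have no per-protocol analysis that fits their time point

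*SAP*

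**What the plan says.** Protocol 9.3 states that the PP population "will include all patients in the mITT without any major/important protocol deviations considered to have an impact on efficacy assessments". It names no endpoint and no visit. Protocol 9.4.1 then says: "The primary endpoint and key secondary endpoints will also be evaluated using the PP population as a sensitivity analysis".

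SAP 5.7 narrows this in three ways:

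- Treatment: the set keeps patients "who did not discontinue the study medication before study day 74". Nothing is said about stopping later.
- Deviations: the set keeps patients who "did not experience any major/important PDs considered to have an impact on efficacy assessments involving lung function at week 12". Only deviations bearing on lung function at Week 12 count.
- Dosing errors found after unblinding: receipt and use of the opposite drug excludes a patient only on condition "that this use occurred prior to week 12".

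SAP Table 2 has a single PP column, and it is marked for secondary endpoints. In the testing order of SAP 7.4, E-RS total (rank 3), SGRQ total (rank 4) and SGRQ responders (rank 7) are all Week 24 endpoints; rank 4, for example, reads "Change from baseline in the SGRQ total score at Week 24". SAP 16.2.4 lists for the key secondary endpoints "Analysis with MI method, as described in Sections 16.2.2 and 16.2.3 of the SAP, based on PP population", under an opening sentence that places the listed analyses at Week 12. SAP 3.3, the list of changes from the protocol, does not mention the PP definition.

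**The concern.** A per-protocol analysis is read as showing the result in patients who followed the protocol up to the time of the endpoint. For Week 12 lung function the SAP 5.7 set does that. For symptoms and quality of life at Week 24 it does not, because no criterion is aimed at the second twelve weeks. A patient who stops drug on Day 75, or who starts a prohibited maintenance therapy at Week 14, is still per-protocol.

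Later stops are foreseen by the design. Protocol 11.6.7 discontinues study treatment after a second or a severe exacerbation, and Protocol 7.2 lets patients who have stopped drug remain in the study and still supply SGRQ data. What is at stake is whether the supportive PP results for E-RS and SGRQ mean what their label says, and whether they exist at Week 24 at all.

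**Working it through.** **1. The plan's own figure.** The only design figure that can be reproduced is the power in Protocol 9.2: SD 250 mL, 500 vs 300 patients, difference 59 mL, two-sided 5%. Standard error = 250 × √(1/300 + 1/500) = 18.26 mL. 59/18.26 = 3.23; 3.23 − 1.96 = 1.27; Φ(1.27) = 89.8%, against 90% stated. It reproduces. It concerns the primary endpoint, and the PP definition does not enter it.

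**2. Endpoint time against PP criteria.**

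| Key secondary endpoint (SAP 7.4) | Defined at | PP criteria aimed at |
|---|---|---|
| Peak FEV₁, morning trough FEV₁, FEV₁ AUC₀₋₄ₕ | Week 12 | Week 12 lung function |
| E-RS total, SGRQ total, SGRQ responders | Week 24 | Week 12 lung function |

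**3. Day count.** SAP 6.4 gives visits a window of ±10 days. 12 × 7 − 10 = 74, so Day 74 is the opening of the Week 12 window. By the same rule the Week 24 window opens at 24 × 7 − 10 = 158. (Counting from nominal Days 85 and 169 moves each by one day.) A patient whose last dose is on Day 74 stays in PP. Days off drug:

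- by Day 169, the end of the Week 24 diary window for patients who leave the study: 169 − 74 = 95 days, 95/169 = 56%;
- by Day 179, the upper limit of the Week 24 spirometry window: 179 − 74 = 105 days, 105/179 = 59%.

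**4. Does the compliance rule close the gap?** SAP 15.1 also counts as non-compliant a patient at or below 50% over the whole study, and non-compliance is a possible reason for PP exclusion. But SAP 15.1 leaves out time after treatment withdrawal, so a patient fully compliant to Day 74 who then stops is not caught. The rule can catch a patient who takes no doses after Week 12 without being recorded as withdrawn: 84/168 = 50% in the 24-week stratum, exactly on the cut-off, and 84/336 = 25% in the 48-week stratum. Even then, SAP 5.7 admits a deviation only if it affects Week 12 lung function.

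**5. The two readings of SAP 16.2.4.**

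- Taken literally, E-RS and SGRQ are analysed in PP at Week 12. The Week 24 key secondary endpoints then have no PP analysis, contrary to Protocol 9.4.1.
- If the opening sentence was meant for lung function only, the Week 24 endpoints are analysed on a set not built for Week 24.

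Either way the passages do not fit together.

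**6. Size, by assumption only.** The documents give no rate of stopping drug or starting prohibited medication between Weeks 12 and 24. If a fraction f of the active PP arm were off drug at Week 24 with no residual effect, the PP difference would be (1 − f) times the on-drug difference: 98%, 95%, 90% and 85% for f = 2%, 5%, 10% and 15%.

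**The case against.** The strongest reply is that SAP 16.2.4 means what it says. Where that section wants other visits it names them: the E-RS analysis excluding zero baselines and the SGRQ analysis excluding post-dose baselines are set at Weeks 6, 12 and 24. On that reading the PP runs are at Week 12 and the set fits them. This stands in part: a reader might infer that a Week 24 PP analysis on the Week 12 set is settled, and it is not. But the literal reading leaves Protocol 9.4.1 unmet at Week 24, so it exchanges one defect for another.

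Second, anchoring a single PP set to the primary endpoint is a defensible choice, and PP is only a sensitivity analysis. Both are true. SAP Table 1 sets a treatment policy strategy on the mITT population, so no gated test uses PP. Average-imputation and tipping-point analyses are also planned. A reader might infer that three confirmatory results are weakened; the documents do not support that.

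Third, a reader might infer that deviations after Week 12 would go unseen. They would not. Protocol 9.4.3 summarises major deviations by category and arm, SAP 1 has the blinded data review report state which patients had each deviation, and SAP 13 summarises COPD medications.

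Fourth, one could apply the 25% withdrawal limit of Protocol 9.2 and derive a number of patients wrongly kept in PP. That limit is a trigger for randomising more patients, concerns leaving the study rather than stopping drug, and is not an expected rate. No patient count follows from it.

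Finally, the blinded data review plan is not among the documents and could hold endpoint-specific rules. SAP 5 nevertheless defines only one PP set.

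**Conclusion.** Wrong as written, with limited effect. The SAP's single PP set has discontinuation, deviation and wrong-drug criteria that end at Day 74 or Week 12, and its deviation test concerns lung function only. It departs from Protocol 9.3 without being listed in SAP 3.3. For E-RS total, SGRQ total and SGRQ responders the plan yields either no PP analysis at Week 24 or one that can include patients off drug for more than half the period (about 95 of 169 days).

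The consequence is confined to a sensitivity analysis: the mITT tests, the hierarchy and the power are untouched. How many patients are involved cannot be derived from the documents, and the dilution percentages in the working are illustrations that assume no residual effect. The conclusion does not depend on any rate. It does assume that the unseen blinded data review plan does not already supply a Week 24 rule.

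**What to change.** - SAP 5.7: keep the present set for the Week 12 lung-function endpoints. Add a Week 24 PP flag for E-RS total, SGRQ total and SGRQ responders, requiring no discontinuation of study drug before the Week 24 window opens (about Day 158), and no important deviation or opposite-drug use affecting symptoms or quality of life up to Week 24. Decide it at the same blinded data review, before unblinding.
- SAP 16.2.4: correct the opening sentence so that each key secondary endpoint is analysed at its own time point on its matching set, and reconcile it with Protocol 9.4.1 and SAP 7.4.
- SAP Table 2: show which PP flag serves which endpoints.
- SAP 3.3: list the changed PP definition.

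The cost is SAP wording and one extra flag at the review. The Week 24 set will be somewhat smaller and more selected on events after randomisation. That is acceptable for a sensitivity analysis but should be kept in mind when its results are set beside the mITT results.
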